Subject Criteria

Inclusion Criteria:

1. Diagnosis of type 1 diabetes mellitus for at least 1 year.
2. Male or female subjects 18 to 65 years of age.
3. Physically willing and able to perform 30 min of exercise (as determined by the investigator after reviewing the subject's activity level).
4. Current use of an insulin pump for at least 3 months.
5. Able and willing to count

[figure not shown]

Figure 2: (a) MotioWear tag based indoor/outdoor tracking and context awareness system. (b) MotioLab software that can be used to do real-time tracking indoors and outdoors. (c) Beacons are placed around the home, creating a wireless mesh that the wearable communicates with. A smart-phone app identifies key regions of interest.

carbohydrates during study period as determined by the investigator after reviewing participant's insulin pump download.

6. A1C <10.5% at the time of screening.
7. Has a smart phone.
8. Willingness to follow all study procedures, including attending all clinic visits.
9. Willingness to sign informed consent and HIPAA documents.

Exclusion Criteria:

1. Female of childbearing potential who is pregnant or intending to become pregnant or breast-feeding, or is not using adequate contraceptive methods. Acceptable contraception includes birth control pill / patch / vaginal ring, Depo-Provera, Norplant, an IUD, the double barrier method (the woman uses a diaphragm and spermicide and the man uses a condom), or abstinence.
2. Any cardiovascular disease, defined as a clinically significant EKG abnormality at the time of screening or any history of: stroke, heart failure, myocardial infarction, angina pectoris, or coronary arterial bypass graft or angioplasty. Diagnosis of 2nd or 3rd degree heart block or any non-physiological arrhythmia judged by the investigator to be exclusionary.
3. Renal insufficiency (GFR < 60 ml/min, using the MDRD equation as reported by the OHSU laboratory).
4. Liver failure, cirrhosis, or any other liver disease that compromises liver function as determined by the investigator.
5. Hematocrit of less than 36% for men, less than 32% for women.
6. History of severe hypoglycemia during the past 12 months prior to screening visit or hypoglycemia unawareness as judged by the investigator. Subjects will complete a hypoglycemia awareness questionnaire. Subjects will be excluded for four or more R responses.
7. Adrenal insufficiency.
8. Any active infection.
9. Known or suspected abuse of alcohol, narcotics, or illicit drugs.

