Up to 75 subjects may be screened in this study. Goal enrollment is 30 subjects.

Withdrawal Criteria

The subject may withdraw at will at any time or at the discretion of the Investigator.

A subject must be withdrawn if the following applies:

1. Hypoglycemia during the treatment period posing a safety problem as judged by the investigator.
2. Hyperglycemia during the treatment period posing a safety problem as judged by the investigator.
3. Protocol deviation having influence on efficacy or safety data as judged by the Investigator.
4. Substantial and repeated non-compliance with trial procedures.
5. Pregnancy.
6. Intention of becoming pregnant.

Visit Procedures

Staff will confirm participant and household do not have COVID-19 or symptoms of COVID-19 prior to conducting any face-to-face visits. In order to minimize face to face contact with participants per OHSU Covid-19 policy, there is the option to complete some visits virtually.

Screening (Visit 1)

Screening will take place within 12 weeks prior to Visit 2. All screening visits will take place at OHSU's Oregon Clinical Translational Research Institute (OCTRI) outpatient clinic, the

Biomedical Engineering Point of Care (BME POC) Laboratory or at the Harold Schnitzer Diabetes Health Center. The subject will be sent the consent form prior to the screening by email so that they can have time to read it fully at their leisure and prepare any questions they might have. Upon arrival at the clinic and prior to any procedures, study staff will explain the study, give the subject ample time to ask questions and consider participation, and ensure that subject voices understanding of the informed consent and study requirements. To minimize the possibility of coercion and to ensure that subject is signing the appropriate version of consent, an informed consent checklist will be used by study staff. After the subject has signed the consent, a copy of the consent/authorization form will be given to the subject. The original will be kept for the source document.

A capillary blood glucose (CBG) will be obtained and measured by a Contour Next glucose meter and recorded after consenting. Prior to measurement of any blood samples, the meter will undergo quality control testing with two different glucose levels, one high and one low, and both values must fall within the accepted range for a meter to be used.

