Subjects will be on study for 28 days. Sensor glucose, activity, exercise, insulin, indoor and outdoor contextual patterns and meal data will be collected during this time. Subjects will wear the Dexcom G6 CGM system along with the Dexcom G6 smart phone application. Subjects will wear a FitBit Ionic (or similar FitBit), Polar, Garmin or Apple Watch physical activity monitor. Subjects will continue to use their own insulin pump. Subjects will be given a MotioWear indoor/outdoor context-aware tracking tag to wear and be shown how to install the MotioWear beacons within their home. Subjects may be asked to plug the MotioWear beacon into their router to improve data uploads. In this visit, they will be asked to complete a lifestyle questionnaire asking about their current exercise habits and blood glucose management. Subjects will be instructed on the use of the T1 DEXI mobile app created by OHSU to capture meal and exercise data along with photos of meals. Subjects will be instructed to take photos of their food the day of and the day after they complete the exercise video. Study staff may contact subjects by phone, text, or email for clarification if the meal photo is difficult to interpret. While at home, subjects will check CBG before and after exercise, for symptoms of hypoglycemia, and

for Dexcom G6 alarms for sensor <70 mg/dL and >250 mg/dL. Subjects will be provided with a Contour Next blood glucose meter for testing capillary blood glucose.

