Subjects will be randomized to complete either aerobic, high intensity interval training, or resistance exercise videos twice weekly at home during weeks 1 and 2 and once weekly during weeks 3 and 4. Subjects will be instructed to complete the exercise for the video sessions in the same location in their home on the same day at approximately the same time. The exercise videos are approximately 30 minutes long. A list of exercises to be performed is provided in Appendix E. Subjects will also ingest a self-selected meal prior to these prescribed exercise sessions. Instructions for the exercise will be provided via video links. Subjects will be instructed to check a CBG before initiating exercise to ensure safety. Subjects will be instructed to consume a snack if glucose is <120 mg/dL and delay exercise until glucose is >80 mg/dL. Also, if glucose is >250 mg/dL, subjects will be instructed to calculate if a correction dose is needed and delay exercise until glucose is <250 mg/dL. Subjects will enter information about exercise into the T1 DEXI app. Subjects will receive reminders via phone or text to complete their exercise and to monitor adherence to protocol. Participants may also receive reminders to enter activity information through the T1DEXI app. Subjects will also be instructed to check a CBG after exercise and consume a snack if needed.

Subjects will consume a high carbohydrate dinner prepared by OHSU Bionutrition once each week on the same day at approximately the same time (but not on the exercise study video days). The meals can potentially be picked up all at once and frozen until use.

Subjects will be able to contact study staff for any issues with the devices. Study staff will follow-up with subjects every 7 days. Subjects may receive text messages from study staff with study reminders/instructions or clarification of meal photos. This visit should take approximately 1.5 hours, depending on subject experience. Participants will be asked to download his/her pump weekly or biweekly during the 28 days on study. This will allow for frequent data capture in case of a battery change or loss of power to the pump which can erase insulin data.

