Statistical methods

The hypothesis of this study is that we will be able to identify contextual patterns in the movement data that will relate to glycemic outcomes. We will use machine learning techniques

including k-means clustering and Gaussian mixture models to group contextual patterns and then relate these groups of patterns with glycemic outcomes including the following:

- Time in hypoglycemia (<70 mg/dL)
- Time in hyperglycemia (>180 mg/dL)
- Time in a target range (70-180 mg/dL)
- Mean glucose
- Glucose variability (standard deviation and coefficient of variance).

We will evaluate if the clusters of contextual patterns are related to differences in glycemic outcome measures using generalized estimating equations, which takes into account correlated data and repeated measures. Data will be analyzed using an intention-to-treat analysis and missing sensed glucose values will be interpolated for up to 20 min segments.

Confidentiality and Protection of Human Subjects

RISKS and BENEFITS

Risks: The risks of the protocol procedures are considered minor. Subjects will be managing their own blood glucose as they normally would.

Risks from exercise include falls, sprains, bruises, very low risk of bone fractures and head trauma. The likelihood of significant harm is quite low.

There is a small risk of sensor fracture, and in such a case, a piece of the sensor could be left in the tissue after sensor removal. For this reason, the study investigator will inspect each removed sensor for the possibility of breakage or fracture. Any evidence of sensor breakage will be recorded and reported to the sensor company.

Benefits: The subject may not directly benefit from being in this study; however, their participation may help to advance automated insulin decision support software.

COSTS:

Subjects will receive \$500 for completion of all study visits. If subjects withdraw early from the study, compensation will be given as follows: \$125 per 7 study days in the study. If the subject completes a partial week, the subject will also receive \$125 for the partial week. There is no compensation for the screening visit. Additional reimbursement will be available for participants who complete protocol requirements to help compensate for their time. The payment amount will be specified in the informed consent form.

Monitoring Entity:

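### Prescribed exercise is weighted 4:2 toward weeks 1-2 and the cluster GEE names no time term, so a cluster that tracks the sessions would absorb part of any glycemic drift over the 28 days

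*Combined protocol and SAP*

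**What the plan says.** Both the Protocol Summary and the Study Start-up Visit (Visit 2) section prescribe the exercise videos "twice weekly at home during weeks 1 and 2 and once weekly during weeks 3 and 4". The observation period is fixed: "Subjects will be on study for 28 days". What is randomized is the type of exercise ("Subjects will be randomized to complete either aerobic, high intensity interval training, or resistance exercise videos"); the weekly schedule is the same for all three types.

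The only step before start-up is screening: "Screening will take place within 12 weeks prior to Visit 2". The study sensor, activity watch, tracking tag, logging app, alarm-triggered glucose checks and prescribed exercise are all introduced at Visit 2. No run-in or baseline period is described.

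The Statistical methods section groups movement-context patterns by k-means and Gaussian mixture models and then states: "We will evaluate if the clusters of contextual patterns are related to differences in glycemic outcome measures using generalized estimating equations". The outcomes are time below 70, time above 180, time in range, mean glucose and glucose variability. The justification offered for GEE is that it handles correlated, repeated data. No covariates are listed: not study week, day or half, and not exercise type either.

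**The concern.** The sessions are there to seed known patterns for the algorithm, and their frequency halves midway through the study. A cluster that recovers those sessions will contain more early days than the clusters it is compared with. A GEE working correlation deals with dependence within a participant; it does not remove a trend in the mean over time. If control improves over the month, the exercise-related cluster will look worse than it is. If control deteriorates, it will look better.

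At stake is the association between context clusters and glycemic outcomes, which is the hypothesis in Statistical methods. The weekly high-carbohydrate dinner does not have this problem: it falls twice in each half, so its share in the first half (2/4) equals that of the other days (12/24).

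**Working it through.** **Inputs from the documents.** 28 days, 14 in each half. Sessions: 2 x 2 = 4 in weeks 1-2 and 2 x 1 = 2 in weeks 3-4, 6 in total. Each video lasts about 30 minutes. Goal enrollment is 30. The plan states no drift, SD, alpha or power, so it has no figure to reproduce.

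**Formula.** Let D be the change in a glycemic outcome between the halves. With no true exercise effect and no time term, the false effect of a cluster that coincides with the sessions has size D x w, where w = (share of exposed time in weeks 1-2) - (share of other time in weeks 1-2).

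**The weight w under four readings of the exposure**

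| Exposure | Calculation | w |
|---|---|---|
| Session days v other days | 4/6 - 10/22 | 0.21 |
| Session day plus next day, no overlap | 8/12 - 6/16 | 0.29 |
| Session day plus next day, the two weekly sessions on consecutive days | 6/10 - 8/18 | 0.16 |
| Session hours v other hours (3 of 672 h) | 4/6 - 334/669 | 0.17 |

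The plan fixes neither the unit of analysis nor the spacing of the two weekly sessions, so the range is about 16-29%. The two next-day rows also assume that no following day crosses from week 2 into week 3.

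**False effect for assumed D, in points of the outcome**

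| w | D = 2 | D = 5 | D = 10 |
|---|---|---|---|
| 0.16 | 0.31 | 0.78 | 1.56 |
| 0.21 | 0.42 | 1.06 | 2.12 |
| 0.29 | 0.58 | 1.46 | 2.92 |

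**How separable exercise and time are.** For session days, the correlation with study half is phi = (4 x 12 - 10 x 2)/sqrt(14 x 14 x 6 x 22) = 28/160.8 = 0.17. The variance inflation from adjusting is 1/(1 - 0.174²) = 1.03. Counting the next day without overlap, phi = 0.29 and the inflation is 1.09. The overlap with time is modest and can be adjusted away.

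**Check by simulation.** Exchangeable GEE, 30 participants x 28 days, 400 runs, true exercise effect 0. Assumed values: outcome 5 points lower in weeks 1-2, between-subject SD 10, within-subject SD 15.

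| Model | Mean estimate | Mean SE | Rejections at 5% |
|---|---|---|---|
| No time term | -1.12 | 1.25 | 17% |
| Study week added | -0.06 | 1.26 | 7% |

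The formula predicts -5 x 0.21 = -1.06 for the first row, which agrees. Adding study week removes the bias and leaves the standard error almost unchanged.

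**The case against.** The strongest reply is that the calculation uses an exposure the plan does not define. The GEE regresses on data-driven clusters of all movement context, not on an indicator for session days. Clusters may mix in habitual exercise and other places and activities that are not front-loaded by the schedule, and such a cluster would carry less of the drift. The documents also give no drift at all, and without one there is no bias. Finally, no covariate of any kind is named, so the missing week term may reflect a short paragraph rather than a decision. The first two points stand and limit the size of the problem. The third does not remove it: the model as written has no time term, and study week is a specific, cheap improvement.

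Some stronger readings are tempting but unsupported:

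- **Participants are new to CGM in weeks 1-2.** A reader might infer this from the start-up training. The device criterion in the eligibility list is "Current use of an insulin pump for at least 3 months"; prior CGM use is neither required nor excluded. The remark "This visit should take approximately 1.5 hours, depending on subject experience" suggests that experience varies. A learning effect is one possible source of drift, not a documented one.
- **Exercise and time are fully confounded.** They are not, because sessions occur in all four weeks.
- **The primary endpoints are biased.** MARE and MRE compare predicted with sensor glucose, and the calculation above does not apply to them.
- **The comparison of randomized exercise types is biased.** All types share one schedule, so this imbalance does not arise between them.
- **Meal information thins out and adds to the bias.** Food photos are tied to session days, but meal logging in the app runs for the whole 28 days, and fewer photos would not produce this bias.

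**Conclusion.** The point holds as a minor, easily corrected weakness in the secondary modelling. From the schedule alone, a cluster that cleanly tracks the prescribed sessions would take up roughly 16-29% of any change in glycemia between the two halves, and 21% in a day-level contrast of session days with other days. Whether that matters depends on a drift that the documents do not give: under an assumed 5-point change, the false effect is about 0.8 to 1.5 points. The conclusion rests on three conditions: that some cluster does track the sessions, that glycemia does drift, and that the GEE is fitted without a time term, as now written.

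**What to change.** In Statistical methods, state that every GEE relating context clusters to glycemic outcomes will include study week (1-4, categorical), so that clusters are compared within the same week. As a sensitivity analysis, report the cluster effects separately for days 1-14 and days 15-28. The prescribed frequency is constant within each half, so those estimates are free of the 4:2 imbalance, although days 15-28 contain only two sessions per participant and will be imprecise. Make this change before the data are examined, since a time term added afterwards could look selective.

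The cost is SAP wording and three extra model terms; in the simulation the standard error rose from 1.25 to 1.26. No visit, schedule or sample-size change is needed. Recording prior CGM use at Visit 2 is optional: the lifestyle questionnaire already covers glucose management, and its items are not shown, so it may already ask this.

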One limitation of current AID systems is that they have no knowledge about the context or environment that a person is currently experiencing. Contextual patterns can potentially improve the performance of an AID by recognizing environments or patterns of living that are related to changes in glucose. The team at OHSU is developing a context-aware glucose prediction algorithm that will capture context data from the patient both indoors and outdoors. This context data will be provided to the algorithm to allow for detecting contextual patterns that might relate to hypo- or hyperglycemia. The goal of this study will be the creation of a data set that will include contextual patterns along with glucose, insulin and physiological data. Participants will complete meals and exercise at specific times. The purpose of the prescribed meals and exercise sessions is to generate ground truth patterns that will be used in the design of the context-aware glucose prediction algorithm.

Primary Objective

- To assess the accuracy of the context-aware glucose prediction by comparing glucose prediction values against the Dexcom G6 CGM values using mean absolute relative error (MARE)
- To assess the accuracy of the context-aware glucose prediction by comparing glucose prediction values against the Dexcom G6 CGM values using mean relative error (MRE).

Study Hypothesis:

- The study hypothesis is that context pattern data will improve the accuracy of the prediction of hypoglycemia and hyperglycemia in the context-aware glucose prediction algorithm.

Primary Endpoints:

- Comparison of the accuracy of hypoglycemia prediction comparing glucose prediction values against the Dexcom G6 CGM values using mean absolute relative error (MARE).
- Comparison of the accuracy of hypoglycemia prediction comparing glucose prediction values against the Dexcom G6 CGM values using mean relative error (MRE).

Study Type

This is a single center randomized prospective study measuring the accuracy of the context-aware glucose prediction against the Dexcom G6 CGM values.

Study Population

[figure not shown]
Study population will be adults with type 1 diabetes, ages 18 – 65 years of age. Older subjects are excluded due to higher risk of unrecognized coronary artery disease. Younger subjects are excluded as it is appropriate to assess safety and efficacy first in the adult population. Thirty subjects will be recruited to participate in studies.

Protocol Summary:

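### Statistical methods gives no analysis of the MARE and MRE primary endpoints and no context-free comparator, so the plan as written does not estimate whether context improves prediction

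*Combined protocol and SAP*

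**What the plan says.** **Hypothesis.** Study Hypothesis states that "context pattern data will improve the accuracy of the prediction of hypoglycemia and hyperglycemia in the context-aware glucose prediction algorithm".

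**Objective.** Primary Objective is wider and not comparative: "To assess the accuracy of the context-aware glucose prediction by comparing glucose prediction values against the Dexcom G6 CGM values", by mean absolute relative error (MARE) and by mean relative error (MRE).

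**Endpoints.** Primary Endpoints is narrower. The first reads "Comparison of the accuracy of hypoglycemia prediction comparing glucose prediction values against the Dexcom G6 CGM values using mean absolute relative error (MARE"); the second is the same with MRE.

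**Stated goal.** The introductory text also describes a data-collection aim: "The goal of this study will be the creation of a data set that will include contextual patterns", with a view to "detecting contextual patterns that might relate to hypo- or hyperglycemia". The prescribed meals and exercise are there to "generate ground truth patterns that will be used in the design of the context-aware glucose prediction algorithm".

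**Analysis.** Statistical methods says the hypothesis is that the study will "identify contextual patterns in the movement data that will relate to glycemic outcomes". It plans k-means and Gaussian mixture clustering of context, then GEE relating clusters to time below 70, above 180 and within 70-180 mg/dL, mean glucose, and glucose variability. CGM gaps of up to 20 minutes are interpolated.

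**Other relevant text.** Recording of Data says the data will serve the analysis of the primary and secondary endpoints, without a method. Study Start-up Visit (Visit 2) randomizes participants to exercise type.

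**The concern.** A claim that context improves accuracy compares two predictors, one with context and one without. The plan names only one predictor and the CGM, and the CGM is the reference against which error is measured. Randomization does not supply the contrast either, because every participant has context recorded and only the type of exercise differs.

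The GEE analysis answers another question. Context clusters could be strongly related to time in range and still add nothing to an algorithm that already uses CGM and insulin. A positive cluster result would therefore not support the Study Hypothesis, and a single MARE for the context-aware algorithm would meet the objective but not test the hypothesis.

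Two further gaps affect any accuracy figure that is reported. Horizon, readings scored and comparator are open, and if they are chosen after results are seen they can change the answer. Patterns from the prescribed sessions are also to be used in designing the algorithm, and nothing keeps the readings used for design apart from those used for scoring. Accuracy scored on design readings could be optimistic.

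**Working it through.** **1. Does any planned analysis produce the primary endpoints?** Statistical methods lists five kinds of outcome: time low, time high, time in range, mean glucose, variability. None is a prediction error, so 0 of 5 is MARE or MRE. Those terms occur only in the opening objectives and endpoints. No summary, model, test, confidence interval or success threshold is given for them.

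**2. Is there a comparator?**

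| Contrast in the protocol | What it compares | Tests improvement from context? |
|---|---|---|
| Prediction against Dexcom G6 | One algorithm with its reference | No |
| Randomized groups | Aerobic, high-intensity interval, resistance | No |
| GEE across clusters | Glycemic outcomes by context cluster | No |

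**3. What is the scope of accuracy?** The objective covers glucose prediction in general, the endpoints hypoglycemia, and the hypothesis both hypo- and hyperglycemia. Statistical methods supplies cut-offs (<70 and >180 mg/dL). It does not state a prediction horizon, or whether measured or predicted glucose decides which readings count as hypoglycemic.

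**4. Could the data support the comparison?** Yes. Protocol Summary has CGM, insulin, activity, meal and context data collected on each participant for 28 days, so both versions could be run offline on the same person.

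**5. What would a time split leave?** Exercise videos are twice weekly in weeks 1-2 and once weekly in weeks 3-4: 2 × 2 + 2 × 1 = 6 sessions. The high-carbohydrate dinner is weekly: 4 in all. Training on weeks 1-2 and scoring on weeks 3-4 would give 4 sessions and 2 dinners for training, and 2 sessions and 2 dinners for scoring, besides all unprescribed days.

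**6. Precision, for illustration only.** The enrollment goal of 30 has no stated alpha, power, effect or SD, so there is no sample-size calculation to reproduce. For a paired difference in participant-level MARE, two-sided alpha 0.05 and 80% power:

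- Normal approximation: (1.960 + 0.842) / √30 = 2.802 / 5.477 = 0.51 SD.
- Noncentral t, 29 degrees of freedom: 0.53 SD.
- If fewer participants contribute (assumed numbers, noncentral t): 24 gives 0.60 SD, 20 gives 0.66 SD, 15 gives 0.78 SD.
- If alpha is split over two endpoints (0.025 each), 30 gives 0.59 SD.

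SD here means the SD of the within-participant difference. The documents do not give it, so these figures cannot be turned into MARE points. They suit MARE better than MRE: MRE is signed, and comparing its size is not an ordinary normal paired difference.

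**The case against.** The best defence is that this is a data-collection study for an algorithm still in development. The protocol says so, participants use their own pumps, and no treatment depends on the result. That aim is legitimate and the cluster analysis serves it. But the same opening section also declares a comparative hypothesis and two primary endpoints, and these need an analysis or a change of wording.

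Several stronger readings are tempting, and the documents do not support them:

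- *The trial is incapable of testing its hypothesis.* The data would allow the test; only the plan for it is missing.
- *No MARE or MRE will ever be reported.* That follows only if Statistical methods is taken alone. Recording of Data commits the data to the primary endpoints, and both are simple summaries that could be reported descriptively. The method and the comparison are what is absent.
- *Hypoglycemia is undefined.* The cut-off is given. The horizon and the rule for selecting readings are not.
- *The source of context is open.* Background on MotioWear System names MotioWear as the tool for this study. Other technologies are mentioned only for future systems. Listing the context inputs is still useful, because activity-watch data could fall on either side.
- *Thirty participants are too few.* No SD or smallest worthwhile improvement is stated, so this cannot be judged.

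The opening part of the protocol is not in the public text and might describe a baseline algorithm. Statistical methods refers to none.

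**Conclusion.** The concern holds as a gap in the analysis plan and must be fixed before results are seen. Following Statistical methods exactly would show whether context clusters relate to glycemic outcomes; it would not estimate whether context makes predictions more accurate. The size of the gap is complete for the Study Hypothesis: the improvement is not estimated at all. For the Primary Objective it is partial, since MARE and MRE against CGM could be reported but have no stated horizon, scoring set or hold-out.

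This conclusion rests on the text alone. The 0.53 SD figure assumes that all 30 participants are scored, one endpoint is tested and participant-level differences are roughly normal. Fewer participants may have enough hypoglycemic readings. Optimism from shared design and scoring readings is a risk that the plan leaves open; the documents do not show that the readings will in fact be shared.

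**What to change.** In Statistical methods:

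1. Make the primary analysis a within-participant comparison of the same algorithm trained and run with and without the context inputs, all other inputs identical. List in advance which inputs count as context: MotioWear location and movement data, and on which side activity-watch data fall.
2. Score both versions on the same held-out CGM readings at a horizon stated in advance. Context is calibrated to each home, and exercise and dinners repeat weekly. If the algorithm is personalised, use a prespecified time split within each participant (earlier weeks for training, later weeks for scoring). If it is meant to transfer between people, use participant-level cross-validation.
3. Use only measured CGM readings as the reference. An interpolated value is not an observed glucose and would score a prediction against an estimate.
4. State whether measured or predicted glucose selects hypoglycemic readings. Report the difference in MARE, and in the size of MRE, with 95% confidence intervals and the number of participants contributing: hypoglycemia first, with hyperglycemia and all readings beside it.
5. State how the two primary endpoints are combined.
6. Report MARE and MRE of the context-aware version alone, for the stated objective.
7. Reconcile the two hypotheses and label the cluster and GEE analysis secondary.

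If the sponsor does not want the comparison, narrow the Study Hypothesis to accuracy against CGM, and keep the hold-out rule and the MARE and MRE report.

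The cost is wording plus training a second version offline on data already collected, with no extra participants, visits or procedures. Narrowing the hypothesis removes the need for the second version.
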